4.3 Control of Systematic Error/Bias

Selection of subjects for enrollment will be made from the investigator's usual patient load. All subjects meeting the eligibility criteria and having signed the ICF will be eligible for enrollment in the study. To control for the potential bias that could be introduced via sponsor classification of endpoint events, an independent Clinical Events Committee (CEC) will adjudicate all potential endpoint events to be used in the data analyses.

4.4 Control of Type-I Error

The primary effectiveness endpoint will be tested at a significant level of 5% (two-sided, or equivalently 2.5% for one-sided test) using the methods described in Section 3.1, and the primary safety endpoint will be analyzed using a two-sided significance level of 5%. As the type-I error level is maintained below 5% for both the primary effectiveness and safety endpoints, the overall type-I error level across both the primary effectiveness and safety endpoints is maintained below 5%. This follows the methodology of the Intersection-Union Test (IUT).

4.5 Methods for Handling Missing Data

When calculating rates of adverse events for specific time intervals, missing and partial dates will be handled as shown below:

Partial Date Description	Action Taken
Entire onset date is missing	The implant procedure date will be used for
	the onset date for device patients and the
	randomization date will be used for Control
	patients.
The month and the day of the month are	January 1 will be used for the month and day
missing but the year is available	of the onset date. However, if the imputed
	date falls before the implant procedure date for
	Device patients and the Randomization date
	for Control patients, then the implant
	procedure date for Device patients and the
	Randomization date for Control patients will
	be used for the onset date.
Day is missing, but the month and year are	The 1 st will be used as the day of the onset
available	date. However, if the imputed date falls before
	the implant procedure date for Device patients
	and the Randomization date for Control
	patients, then the implant procedure date for
	Device patients and the Randomization date
	for Control patients will be used for the onset
	date.

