3.2 Primary Safety Endpoint

The primary safety endpoint is non-procedural bleeding through 36 months (ISTH major bleeding and clinically relevant non-major bleeding). This endpoint is defined as the Kaplan Meier estimate of time to first occurrence of non-procedural ISTH major bleeding or clinically relevant non-major bleeding through 36-months. Non-procedural events are those occurring after 3 days, calculated from implant or attempted implant date for Device patients and from date of randomization for Control patients. This endpoint will be tested for superiority of WATCHMAN vs Control.

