7.4 Clinical Events Committee

An independent Clinical Events Committee (CEC) will adjudicate all potential primary and secondary endpoints. CEC responsibilities, membership, meeting frequencies and procedures are outlined in the CEC charter. The CEC will make the final adjudication and classification of the

primary and secondary endpoints per the CEC charter, and the CEC determinations will supersede the site-reported data and sponsor classifications in all analyses of the primary and secondary endpoints.

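### The SAP's missing-date rule, if applied to the primary safety endpoint, drops every bleed with no onset date by placing it inside the 3-day procedural window

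*SAP*

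**What the plan says.** SAP 4.5 introduces its date rules with "When calculating rates of adverse events for specific time intervals, missing and partial dates will be handled as shown below". There are three:

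- **Whole onset date missing.** For Device patients, "The implant procedure date will be used for" the onset date. For Control patients it is the randomization date.
- **Only the year known.** "January 1 will be used for the month and day" of onset. The date moves to the implant date (Device) or randomization date (Control) only if January 1 falls before it.
- **Only the day missing.** The 1st of the known month is used, with the same floor.

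SAP 3.2 defines the primary safety endpoint as "time to first occurrence of non-procedural ISTH major bleeding or clinically relevant non-major bleeding through 36-months", and sets the window thus: "Non-procedural events are those occurring after 3 days, calculated from implant or attempted implant date for Device patients and from date of randomization" (the latter in the Control arm). The imputation dates in 4.5 are therefore also the dates from which the 3-day window runs.

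On adjudication, SAP 7.4 says that "the CEC determinations will supersede the site-reported data and sponsor classifications in all analyses of the primary and secondary endpoints". Neither that section nor Protocol 23.3 says that the CEC sets a missing onset date, or decides procedural status when the date is unknown.

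**The concern.** Imputing an unknown onset to the earliest possible date is usually the cautious choice in a time-to-event analysis: the event is kept and its time is shortened. Here the endpoint begins only after day 3, so the earliest date is the one date range in which the event does not count. The same rule therefore removes the event.

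The endpoint is one of two that must both be met for study success (SAP 3.3.5), and it is a superiority claim. A lost clinically relevant non-major bleed is not picked up by another hypothesis test, because the secondary endpoint takes ISTH major bleeds only.

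There is also an undefined case. Device subjects with no implant attempt (the Intent class, Protocol 10.2.3.1) are analysed by intention to treat, but they have no implant or attempt date. For them neither the imputed date nor the 3-day window is defined.

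**Working it through.** **1. The plan's own power figure.** Inputs from SAP 3.2.2: 14% Device, 20% Control at 36 months, two-sided alpha 5%, attrition 20%, N = 1600. Allocation is 1:1 (Protocol 11.6), so 800 per arm.

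- Hazard ratio = ln(0.86)/ln(0.80) = 0.676.
- Expected events per arm = 800 × λ/(λ+μ) × [1 − (1−F)(1−0.20)], with λ = −ln(1−F) and μ = −ln(0.80) over 36 months.
- Device: 800 × 0.1508/0.3740 × (1 − 0.86×0.80) = 100.7.
- Control: 800 × 0.5 × (1 − 0.80×0.80) = 144.0.
- Total = 244.7.
- Schoenfeld power = Φ(√(244.7/4) × |ln 0.676| − 1.96) = 86.5%. Freedman's formula gives 85.7%. The stated 86.4% is reproduced.

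**2. What the written rule does to a true non-procedural bleed (days 4 to 1095).** A bleed leaves the endpoint if its imputed date is the anchor date or 1-3 days after it.

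- *Whole date missing:* the imputed date is day 0, so 100% are lost.
- *Year only:* the bleed is lost if it falls in the same calendar year as the anchor, or if January 1 of its year falls 1-3 days after the anchor. A rough count for the same-year part is (182 − 3)/1095 = 16.3%.
- *Day missing:* the same logic by calendar month; roughly 12/1095 = 1.1%.

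Enumerating every anchor date in a calendar year gives:

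| Event-time assumption | Year only: lost | Day missing: lost |
|---|---|---|
| Uniform over 36 months | 16.7% | about 1.3% |
| Exponential with 20% attrition, 14% rate | 19.2% | 1.6% |
| Exponential with 20% attrition, 20% rate | 19.7% | 1.7% |

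All other partially dated bleeds stay in the endpoint, with an onset no later than the true one.

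**3. Effect on the test.** The documents give no frequency of missing dates, so the share f of endpoint bleeds lost is an assumption, shown over a range.

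*Equal loss in both arms.* Rates become 14%×(1−f) and 20%×(1−f); events and power follow as in step 1.

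| f | Rates | Hazard ratio | Events | Power |
|---|---|---|---|---|
| 0 | 14.0% / 20.0% | 0.676 | 244.7 | 86.5% |
| 1% | 13.86% / 19.8% | 0.676 | 242.2 | 86.1% |
| 2% | 13.72% / 19.6% | 0.676 | 239.8 | 85.7% |
| 5% | 13.3% / 19.0% | 0.677 | 232.4 | 84.4% |
| 10% | 12.6% / 18.0% | 0.679 | 220.1 | 82.0% |

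*Loss in one arm only.* These are extreme cases that show the direction of the effect, not forecasts.

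| f | Device-only loss, true rates both 20%: chance of a false finding for Device (nominal 2.5%) | Control-only loss, true rates 14% / 20%: power |
|---|---|---|
| 2% | 3.8% | 81.9% |
| 5% | 6.9% | 73.1% |
| 10% | 16.1% | 54.9% |

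**The case against.** **Scope.** SAP 4.5 is written for adverse event rates in specific time intervals, while the primary safety test is a log-rank test on adjudicated events. The SAP does not say that 4.5 governs it. This stands, and it is why the point is conditional. But the endpoint is itself a bleeding event in a defined interval, and SAP 5.6 deals with censoring of drop-outs, not with onset dates. A programmer with an undated bleed would have only 4.5 to follow.

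**Adjudication.** The CEC reviews a dossier that may include source documents and confirms inclusion in the endpoints (Protocol 23.3), so it may settle many cases. That is likely in practice but not written, and SAP 3.2 defines non-procedural by day count alone.

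**Frequency.** A reader might infer that undated bleeds are common because scheduled visits are about a year apart after month 3. The documents do not support that. A clinically relevant non-major bleed requires medical intervention, hospitalization or increased care, or a face-to-face evaluation (Protocol 29.2.3.2), which normally leaves a dated record. All bleeds are reportable (Protocol 21.1), the adverse event form carries a date (Protocol 21.4), and discrepancies are queried (Protocol 15.1). Wholly undated bleeds should be few.

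**Partial dates.** A reader might also infer that every bleed with an incomplete date is deleted. It is not: at least 80% of year-only bleeds and 98% of those missing only the day stay in.

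**Mitigation.** The endpoint is time to first event, so a subject with another dated non-procedural bleed still counts. Major bleeds remain in the secondary endpoint, which includes procedural bleeding. Both points stand, but they cover only some of the affected subjects.

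**The remedy is also an assumption.** Counting unresolved bleeds as non-procedural could turn true implant bleeds into Device-arm endpoint events. This is fair; hence CEC determination comes first, and the fallback is tested in both directions.

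**Conclusion.** The point holds in a limited form. Read together, SAP 4.5 and 3.2 exclude every wholly undated bleed from the primary safety endpoint if 4.5 is applied to it, and nothing else in the SAP prevents this. Partial dates are affected only when the imputed date lands before the anchor or within 3 days after it: about 16-20% of year-only and 1-2% of day-missing bleeds, assuming anchor dates spread evenly over the year and uniform or exponential event times.

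The likely effect on power is small: with an assumed equal loss of 1-5% of bleeds, from about 86.5% to 86.1-84.4%.

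It would be tempting to conclude that the rule favours the device. The documents do not support that. The rule is parallel in both arms, each anchor matches that arm's own endpoint window, and nothing suggests that dates will be missing more often in one arm. Bias arises only if missingness differs, and its direction is then unknown. The reason to act is that a written rule gives the wrong answer when followed on an endpoint required for study success, and it is easily corrected before the data are analysed.

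**What to change.** Add one paragraph to SAP 4.5:

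1. For bleeding endpoints, the CEC determines onset date and procedural status from source documents, and those determinations are used in the analysis.
2. Where the date stays incomplete, date imputation alone does not classify a bleed as procedural. The bleed counts as non-procedural, at the earliest date after day 3 compatible with what is known, unless the CEC adjudicates it procedural.
3. Two sensitivity analyses: one treating unresolved bleeds as procedural, one using the latest compatible date.
4. Name the anchor date for Device subjects with no implant attempt, for both the imputation and the 3-day window. SAP 3.2.3 (all randomized subjects) and SAP 4.1 (Device subjects treated as assigned) also differ on whether these subjects are in the safety analysis; align them at the same time.

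Report by arm the number of bleeds with wholly and partly missing dates, so that a reader can see whether the rule mattered. The cost is the added text, a line in the CEC charter and two short reruns of the log-rank analysis. No new data collection or change in sample size is needed.

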5 SUPPORTING DATA ANALYSES

The analyses described in this section will be performed at a time determined for the primary effectiveness and safety endpoint analysis. No adjustments for multiple comparisons will be made. Additional analyses will be performed as appropriate.

Data collected related to COVID-19 will be assessed. If there is significant impact of COVID-19 on results, additional analyses (e.g.: sensitivity) will be performed to assess the impact of COVID-19 on the study results according to regulatory guidance.

5.1 Description of Baseline Variables

Baseline demographic and clinical variables will be summarized for each of the treatment groups for both the intent-to-treat and per protocol populations. All continuous variables will be summarized as means, medians, standard deviations and interquartile ranges and compared between treatment groups using one-way analysis of variance (ANOVA) or the non-parametric Kruskal-Wallis test. Categorical variables will be summarized as frequencies and percentages and compared between treatment groups using Pearson's χ^2 test or Fisher's exact test, as appropriate. Ordinal variables will be compared using Cochran-Mantel-Haenszel test with row mean scores.

A by-subject listing of key demographic data and baseline characteristics, including variables used for stratification will be provided.

5.2 Subgroup Analyses

Primary effectiveness and safety endpoint results will be summarized. Additionally, treatment groups compared based on the following subgroups:

- Sequential vs Concomitant patients
- Male vs female
- Age at time of consent (< 75 years vs. ≥ 75 years)
- Stroke risk (CHA₂DS₂-VASc score 2-3, 4-5, and >5)
- Bleeding risk (HAS-BLED scores of 0, 1-2, and > 2)
- AF type at baseline (paroxysmal, persistent, permanent)
- Implanting image techniques (TEE vs CT for core lab data)

Time-to-event curves will be constructed for each treatment group, HRs and log-rank test p-values will be calculated within each subgroup, and subgroup by treatment interactions will be tested using Cox regression.

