11.2. Data Collection - Randomized Subjects

For all Intent, Attempt, and Implant subjects (successfully received the WATCHMAN FLX Device) all visits are required, as defined in Table 11.2-1. However, Intent and Attempt subjects do not require LAA imaging at 3 and 12 months.

Study procedures and follow-up visits will occur as follows:

Table 11.2-1: Randomized Subject Study Visits

Visit	Timeframe			
Consent	Must be performed within 30 days prior to randomization			
Randomization and Implant	- Prior ablation (Sequential group) – randomization must be performed between 90 and 180 days after the most recent AF ablation procedure. WATCHMAN FLX implant must be performed within 10 days following randomization - Planned ablation (Concomitant group) – the ablation +/- WATCHMAN FLX implant must be performed within 10 days of randomization			
Pre-procedure LAA Imaging (TEE or CT)	- Optional for TEE guided WATCHMAN FLX implants - Required for ICE guided WATCHMAN FLX Implants (must be performed after randomization and prior to implant). These LAA imaging will be collected according to the Imaging Manual and submitted to the Core Lab for review			
3-Month Follow-up	90 ± 15 days from randomization			
12-Month Follow-up	365 ± 30 days from randomization			
24-Month Follow-up	730 ± 60 days from randomization			
36-Month Follow-up	1095 + 60 days from randomization - this follow-up must occur on or after 1095 days and on or before 1155 days			

Note: Baseline data collection not available prior to consent must occur within 30 days prior to randomization. Study-specific procedures that are not standard of care must only be performed after the patient has signed informed consent.

Table 11.2-2: Data Collection Schedule

	Baseline Assessment (Prior to Randomization)	Index Procedure (Ablation Procedure +/- WATCHMAN FLX)	Follow-up Visits****			
Procedure/Assessment			3-Month Follow- up	12-Month Follow- up	24-Month Follow-up	36-Month Follow-up
Informed consent process, including informed consent signature date	X					
Demographics	X					
Physical assessment	X	DG and CC	X	X	X	X
Medical history	X					
Ablation Information	X	CC	0	0	О	0
Device information		DG				
Procedure information and discharge assessment		DG and CC				
TTE	X***					
Pre-procedure LAA imaging (TEE or CT)		DG^				
Implant Procedure TEE/ICE		DG				
Follow-up LAA imaging (TEE or CT)			DG*	DG*	О	О
Brain Imaging (CT or MRI)	O**	O**	O**	O**	O**	O**
Serum Creatinine or GFR/eGFR	X					

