11.7. Index Procedure

For all patients undergoing ablation and/or WATCHMAN FLX implantation, the following data will be collected:

 Physical assessment including vital signs, weight, and rhythm at time of the procedure

- Current medication regimen review for the use of antiplatelet, NSAID, anticoagulant, and antiarrhythmic medications
- Ablation information (patients undergoing Ablation) including ablation type, success, and rhythm post-ablation
- Adverse events experienced at index procedure and since enrollment. Refer to Section 21 for detailed information on Safety reporting
- Discharge information (date, time)

For patients undergoing WATCHMAN FLX implantation, the procedure should be performed using standard of care methods established by the investigational site (e.g., sterile technique, personnel requirements, etc.). Implantation of the WATCHMAN FLX Device shall only be performed by study physicians trained in percutaneous and transseptal procedures who have completed the WATCHMAN and/or WATCHMAN FLX physician training programs. Refer to the WATCHMAN FLX Instructions for Use (IFU) for detailed instructions regarding the implantation and use of the WATCHMAN FLX Device.

Notes:

- 1. TEE is recommended for implant procedures; however, intracardiac echocardiography (ICE) is an acceptable alternative and may be used if the following conditions are met:
 - Pre-planning LAA imaging using TEE or CT must be completed prior to the implant procedure.
 - The implanting physician must have performed ≥ 25 WATCHMAN and/or WATCHMAN FLX procedures that involve the use of ICE.
 - If ICE is used, the site must perform pre-planning LAA imaging and must specify in the eCRF what imaging modality was used.
- 2. Do not proceed with the WATCHMAN FLX implant if the following is observed on TEE/ICE or fluoroscopy:
 - Intracardiac thrombus, LAA sludge (gelatinous, non-adherent, intracavitary echodensity more layered than dense spontaneous echo contrast (SEC) seen continuously throughout cardiac cycle) or dense SEC.
 - Complex atheroma with mobile plaque of the descending aorta and/or aortic arch.
 - The LAA anatomy will not accommodate a WATCHMAN FLX closure device.
 - High-risk PFO not detected at baseline.

Additional data collected for patients undergoing WATCHMAN FLX implantation:

- WATCHMAN FLX Device usage information, including device size and compression post-implant (Device Group only);
- Access System(s) usage information

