11.10.1. Baseline Transthoracic Echocardiogram (TTE)

The baseline TTE will be done to evaluate all exclusion criteria and to confirm subject eligibility. Criteria obtained from a cardiac imaging performed within 180 days prior to randomization may be used if all the exclusion criteria can be evaluated. If all exclusion criteria were not obtained on the prior cardiac imaging, a TTE will have to be conducted at baseline. If a significant cardiac event occurs after the cardiac imaging which causes a change in cardiac status [i.e., major Congestive Heart Failure (CHF) decompensation] the baseline TTE must be repeated after informed consent and prior to randomization.

If a subject meet any of the echo exclusion criteria, they should be screen failed and withdrawn immediately.

11.10.2.Implant and Follow-Up Imaging (TEE/ICE/CT)

All protocol required LAA imaging will be performed in accordance with the Core Lab Imaging Manual.

Implant LAA imaging (TEE recommended) will allow the investigator to obtain proper measurements of the LAA to correctly size the device, confirm device release criteria are met prior to device release, document absence of intracardiac thrombus, and confirm adverse events have not occurred during the implant procedure (i.e., pericardial effusion).

TEE is recommended for implant procedures; however, ICE may be used by investigators that meet the following conditions:

- Pre-planning with TEE or CT must be performed prior
- The implanting physician has performed ≥ 25 WATCHMAN and/or WATCHMAN FLX procedures that involve the use of ICE

The 3-month and 12-month LAA imaging (TEE recommended) is conducted to assess flow through and around the WATCHMAN FLX Device and to verify there is no device related thrombus (DRT) on the surface of the device. Adequate LAA seal is defined as demonstration of peri-device flow ≤5 mm around the margins of the WATCHMAN FLX Device.

Copies of all protocol required LAA imaging must be provided to the core lab per the Imaging Manual. LAA Imaging must be saved and available for review in the subject's medical or study file. Certain information from the LAA imaging conducted during the course of the study, including any non-protocol required LAA imaging (such as that performed in the context of an embolic event; see **Section 11.11.2**), will be captured on the study case report forms and submitted to the core lab. All study required images must be identified as defined in the Imaging Manual.

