11.13. Device Seal

For those subjects receiving a WATHCMAN FLX device, if adequate device seal (i.e., no leak > 5mm) is not obtained as demonstrated by the 3-month post-implant imaging (TEE or CT), the decision to continue or stop OAC and/or aspirin is at the discretion of the investigator and should be based on the individual subject's risk/benefit analysis (if possible, OAC should generally be prescribed). Follow-up imaging may be performed prior to the 12-month visit to reassess seal and inform the decision to stop OAC and/or aspirin. If device seal is not obtained as demonstrated by the interim or the 12-month imaging (TEE or CT), the decision to continue or stop OAC and/or aspirin is at the discretion of the investigator (if possible, OAC should generally be prescribed).

Note: Clinical study data establishing safety and effectiveness are based on demonstration of peri-device flow ≤5 mm as a measure of adequacy of LAA seal. Per the WATCHMAN FLX IFU, if adequate seal is not demonstrated, decision to discontinue OAC is at physician discretion provided that any leak demonstrated is ≤ 5 mm. Non-approved measures/procedures to improve seal (e.g. 'kissing' WATCHMAN, vascular plugs, endovascular coils, etc.) must not be attempted during the course of this study.

TEE is recommended for follow-up imaging, but CT is an acceptable alternative. However, if findings suspicious for significant peri-device leak (PDL) (e.g. leak width > 3mm) is noted on CT at follow-up, a TEE must be performed to determine if therapy is required.

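### The implant-imaging subgroup in SAP 5.2 has no scheduled value in Controls, so its treatment comparison and interaction cannot be estimated as specified

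*SAP*

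**What the plan says.** SAP 5.2 gives seven subgroup factors for the primary effectiveness and safety endpoints. Six are known at or before randomization: ablation timing, sex, age, stroke risk, bleeding risk and AF type. The seventh is "Implanting image techniques (TEE vs CT for core lab data" (closing bracket follows).

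The instructions cover the whole list without exception. The SAP wants "treatment groups compared based on the following subgroups", then says that "HRs and log-rank test p-values will be calculated within each subgroup" and that "subgroup by treatment interactions will be tested using Cox regression".

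The protocol describes the imaging as follows:

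- **Implant.** The schedule row in Protocol 11.2 is "Implant Procedure TEE/ICE", marked for the Device Group only. Protocol 11.7 says "TEE is recommended for implant procedures; however, intracardiac echocardiography (ICE) is an acceptable alternative", and 11.10.2 repeats this with conditions on the operator.
- **Pre-procedure.** TEE or CT, for Roll-In and Device Group subjects (Protocol 11.2 and 11.10).
- **Follow-up at 3 and 12 months.** TEE or CT, for successfully implanted subjects only (footnote to the schedule in 11.2). Protocol 11.13 says "TEE is recommended for follow-up imaging, but CT is an acceptable alternative".
- **Core lab.** It receives pre-planning images for ICE-guided cases and the implant, 3-month and 12-month images (Protocol 15.3).

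The protocol's own subgroup list (13.3.3) has six factors. Imaging technique is not one of them.

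**The concern.** A treatment-by-subgroup analysis needs a factor that can be observed in both arms and that treatment does not determine. Implant imaging is neither. It exists because a subject was assigned to, and went on to, an implant. Control subjects take oral anticoagulation and have no scheduled appendage imaging of any kind.

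A programmer who follows SAP 5.2 literally would get a model that cannot return the requested interaction, or would have to improvise. The obvious improvisation is to set TEE-imaged Device subjects against all Controls and then CT-imaged Device subjects against the same Controls. Those Device subsets are formed after randomization by site, operator and patient characteristics. The resulting hazard ratios would stand in the same table as valid baseline subgroups, for both primary endpoints, with nothing to mark them as a different kind of comparison.

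**Working it through.** The plan gives no sample size, power or alpha for this subgroup, so there is no stated figure to reproduce. The check is whether the requested quantities can be estimated.

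**Inputs.** 1600 randomized 1:1 (Protocol 8.1 and 11.6), so 1600/2 = 800 per arm. The documents do not give the share of Device subjects imaged by CT. I assumed 5%, 20% and 50%, which is 40, 160 and 400 of 800.

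**Model implied by SAP 5.2.** Hazard = h0(t) × exp(b1·T + b2·C + b3·T·C), where T = 1 for Device and C = 1 for CT. A Cox model has no intercept, so the rank that matters is that of the centered columns T, C and T·C. All three effects need rank 3.

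1. **Controls missing on C.** Only Device subjects remain. T is always 1, so its centered column is zero, and T·C equals C. Rank is 1 of 3. Neither the treatment effect nor the interaction can be estimated.
2. **Controls all coded to the reference level (C = 0).** C = 1 occurs only when T = 1, so T·C again equals C. Rank is 2 of 3. The interaction cannot be separated from the CT main effect. The CT stratum holds no Controls, so it has no hazard ratio or log-rank test. The TEE stratum becomes a Device subset against every Control.
3. **A factor seen in both arms**, such as sequential versus concomitant ablation. The three columns are distinct. Rank is 3 of 3, and the interaction can be estimated.

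The ranks were computed at all three assumed CT shares and did not change. The result comes from the structure of the data, not from the unknown share.

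**Does another time point help?** The SAP label can be set against each imaging occasion in the protocol:

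| Occasion | Modalities | Scheduled in | Relation to randomization |
|---|---|---|---|
| Pre-procedure | TEE or CT | Device Group, Roll-In | After (randomized subjects) |
| Implant | TEE or ICE | Device Group | After |
| 3 and 12 months | TEE or CT | Implanted subjects | After |

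No row supplies a Control value. Roll-In subjects are not randomized and are analyzed separately, so they do not help. Using the 3- or 12-month scan would add a further fault: subjects would be grouped by something learned after follow-up for the endpoint had begun, and Intent and Attempt subjects would drop out because they are not required to have those scans.

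**The case against.** The best defence concerns the label. Because implants are guided by TEE or ICE, a reader might infer that the CT level is empty and the item simply wrong. The documents do not support that as a firm statement. The item refers to core lab data, the core lab also receives pre-planning and follow-up images, and TEE and CT are the named modalities on those occasions. The pre-procedure row even sits in the index-procedure column of the schedule. On that reading the levels are real and the wording is loose. This defence stands, so the label is best called ambiguous. It does not rescue the analysis, because those images too are scheduled only around an implant.

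A reader might also infer that exactly zero Controls could have a value. That goes too far. Controls may cross over to a device, with 3- and 12-month imaging recommended, and remain Controls for follow-up (Protocol 12). SAP 4.2 keeps in all analyses those who have appendage closure before a primary event. Appendage imaging is encouraged in any subject after a stroke or systemic embolism (Protocol 11.11.2). A few Controls could therefore have images, and software might then return a number. They would not form a valid Control stratum: crossover occurs after randomization and is selective, and post-event imaging follows the very outcome being analyzed.

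A third inference is that the plan wrongly omits a TEE-versus-ICE comparison. Nothing in the documents names that as a question of interest, and SAP 5 leaves room for additional analyses. Whether to make it is the sponsor's choice.

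**Conclusion.** The point holds. SAP 5.2 asks for within-subgroup treatment comparisons and a treatment interaction on a factor that has no scheduled value in Controls and is set after randomization. On scheduled data the model has rank 1 or 2 where 3 is needed, whatever the CT share. Nothing elsewhere in the protocol or SAP makes an exception for this item. Separately, the label leaves both modality and time point open.

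The conclusion rests on the protocol's imaging schedule being what defines the factor. It does not mean that no imaging analysis is possible: a description within Device subjects can be produced.

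Severity is low. This is one of seven supporting subgroups, without multiplicity adjustment, and it enters neither the testing hierarchy in SAP 3.3.5 nor the rule for study success. A reader should not infer any effect on the primary conclusions.

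**What to change.** Remove the imaging item from the treatment-subgroup list in SAP 5.2. This also brings the list into line with Protocol 13.3.3 on this item.

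If the sponsor wants an imaging analysis, restate it elsewhere in SAP Section 5 as descriptive and confined to Device subjects, with no Control comparison and no treatment interaction. Name the modality contrast and the time point: TEE versus ICE for implant guidance, or TEE versus CT for pre-procedure or follow-up core lab images. State which Device subjects are included (for example, implanted subjects with a core lab reading).

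The cost is SAP wording. No new data collection should be needed: implant and follow-up images already go to the core lab, and sites that use ICE must record the imaging modality on the case report form. For pre-procedure imaging, core lab submission is required only in ICE-guided cases, so an analysis at that time point should say that it is limited to them.
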